Historically the distinction between NMO and MS has been extensively debated but following the discovery of NMO-IgG or aquaporin-4 (AQP4) antibody, which is a circulating antibody which targets the dominant water channel in the central nervous system (Lennon et al., 2005), separate classifications have been developed. The 2006 Wingerchuk NMO diagnostic criteria have been established and shared globally (Wingerchuk et al 2006). NMOSD includes individuals manifesting *with* recurrent myelitis or recurrent optic neuritis or with a variety of signature brain syndromes, such as intractable vomiting and hiccups, and is diagnosed by 'Criteria 2007' (Wingerchuk et al., 2007). *In the most recently published diagnostic criteria, the overarching term*

NMOSD was selected to unify traditional NMO and modern NMOSD definitions (Wingerchuk et al. 2015).

In light of the non-reversibility of the neurological deficit associated with relapses, maintenance immunosuppression has become standard practice. The current standard in the United States (US), European Union (EU), Canada and Pacific Rim countries outside of Japan, is to achieve and maintain remission with corticosteroids and then gradually withdraw them in favor of a non-steroid immunosuppressant, although some patients need a low dose of oral steroids to maintain remission. Treatment with a variety of different agents has been described although no randomized comparisons of different therapies exist. Treatment approaches for prevention of attacks include systemic immunosuppression with azathioprine or mycophenolate mofetil. Methotrexate use has also been reported, as is use of mitoxantrone chemotherapy. In terms of biologic agents, rituximab, which is not approved for treatment of MS or NMO, is widely used by clinicians in some countries. The use of tocilizumab (Araki et al. 2012, Azyenberg et al. 2013, Kieseier et al. 2013) in NMO *has* also been reported.

Limited observational evidence suggests that typical MS treatments, including interferon (IFN)- β , natalizumab and fingolimod, are not effective in NMO and may be harmful when used to treat these patients. Unlike MS, disability in NMO is directly tied to the number and severity of relapses. There *remains* an unmet medical need to develop *additional therapeutic options to reduce the likelihood* of relapses.

1.1.2 Interleukin 6 as a Target Molecule for the Treatment of NMO and NMOSD

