4.3.2.1 Satralizumab and Placebo: Double-blind period

The patient will receive an SC injection of satralizumab or placebo at Weeks 0, 2 and 4, and Q4W thereafter during the double-blind period. The double-blind period ends when either the patient has a protocol-defined relapse which is adjudicated by CEC, the total number of registered relapses is 44 or 1.5 years after the date of randomization of the last patient enrolled, whichever comes first.

Patients who experienced a relapse during the double-blind period should continue the double-blind period regardless of rescue therapy unless the patient experiences a relapse which is adjudicated by CEC as a protocol-defined relapse, and will continue administration of study treatment at the discretion of the Investigator.

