4.2 General Presentation Considerations

The analyses periods are defined as follows:

- Study duration of double blind period for efficacy analysis
 - Study duration of double-blind period starts on the day of the randomization. The double-blind period ends on the earliest day of 1) clinical cutoff date (CCOD), 2) the day before the first treatment in the extension period, 3) the end of the study, or 4) last contact for patients lost to follow up.
- Double blind period for safety analysis
 - Double blind period starts on the day of first dose of study drug. The double-blind period ends on the same day as the efficacy analysis.
- Study duration of SA237 exposure for safety analysis (for All SA237 analysis)
 - Study duration of SA237 exposure starts on the day of first dose of SA237. Study duration of SA237 exposure ends on the earliest day of 1) CCOD, 2) the end of the study, or 3) last contact for patients lost to follow up.

The definition of summaries by visit is as follows:

- Summaries by visit for double blind period
 - Baseline is defined as the latest data before or on the date prior to first administration with either placebo or SA237. Summarized visits except for baseline are defined as follows. Irregular visits such as unscheduled visit between week X, dose outside the visit window (DOW), extra visit at relapsing, and the end of the study are out of scope. Week X visits are

TP-GDO-WW-016-01 Confidential Version 7.0 Effective Date: 28Aug13 Version Date: 28NOV2018

Related to: SOP-GDO-WW-019

Related to: SOP-GDO-WW-019

directly used for categories of time. In other words, time window is not applied. If there are the same visits data, one representative assessment nearest to the scheduled visit day will be summarized.

- Summaries by visit for All SA237 analysis
 - Baseline is defined as the latest data before or on the date prior to first administration of SA237. Summarized visits except for baseline are defined as follows. Irregular visits such as unscheduled visit between week X, dose outside the visit window (DOW), extra visit at relapsing, and the end of the study are out of scope. Time window is applied as if visit schedules continue in the double-blind period. Middle of each specified day of visit will be used for the range of time window of each visit. One representative assessment nearest to the specified day of visit in time window of each visit will be summarized

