4.10.1.3 Handling of Dropouts or Missing Data

TP-GDO-WW-016-01 Confidential Version 7.0 Effective Date: 28Aug13 Version Date: 28NOV2018

For details on censoring rule for the primary endpoint, see section 4.10.2 and handling of missing data for the key secondary efficacy endpoints see section 4.10.3.

For secondary continuous endpoints, a Mixed-effects model repeated measures analysis incorporating all data in double blind period will be used to utilize all the data collected over time with consideration of the variance-covariance matrix of the repeated measures. This method allows a general unstructured variance-covariance matrix and will include data from patients with incomplete data from some scheduled time points.

For FACIT fatigue questionnaire, if there are less than 7 responses recorded, then the total fatigue score will be considered missing. If there are 7 or more responses recorded, then the total fatigue score for that questionnaire will be calculated as the average of the non-missing scores multiplied by 13.

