4.10.3.1 Key Secondary Endpoints

 Analysis of change in VAS for pain score from baseline to week 24 using ANCOVA (BOCF).

TP-GDO-WW-016-01 Confidential Version 7.0 Effective Date: 28Aug13 Version Date: 28NOV2018

Related to: SOP-GDO-WW-019 Page 24 of 60

• Analysis of change in FACIT fatigue scale score from baseline to week 24 using ANCOVA (BOCF).

The ANCOVA will include treatment group as fixed effect; the baseline measurements and stratification variables as covariates.

The missing data will be imputed by baseline observation carried forward (BOCF) method.

Additionally, sensitivity analyses using different imputation methods (random hot deck, imputation using OLE baseline/withdrawal visits) and MMRM using all collected data during the double-blind period will be performed as follows:

Random hot deck:

Random hot deck imputation method using a regression based approach will be conducted. In this imputation method, missing values will be replaced with values from a similar responding unit.

Imputation using OLE baseline/ withdrawal visits:

VAS for Pain and fatigue are assessed at OLE baseline visit for patients entering into OLE and the withdrawal visit for patients discontinuing from treatment. Missing values for patients that do not have a Week 24 assessment, but for which a pain /fatigue assessments is available between study days 85 and 252 from an OLE baseline or withdrawal visit, will be replaced with these values. The remaining missing values will be imputed using BOCF.

- Analysis of change in VAS for pain score from baseline to week 24 using ANCOVA by random hot deck imputation method.
- Analysis of change in FACIT fatigue scale score from baseline to week 24 using ANCOVA by random hot deck imputation method.
- Analysis of change in VAS for pain score from baseline to week 24 using ANCOVA with imputation using OLE baseline/ withdrawal visits
- Analysis of change in FACIT fatigue scale score from baseline to week 24 using ANCOVA with imputation using OLE baseline/ withdrawal visits

The following summary tables and analyses including all available visits in the double-blind period will also be provided as exploratory analyses:

- A summary table of change in VAS for pain score from baseline to every 24 weeks.
- A summary table of change in FACIT fatigue scale score from baseline to every 24 weeks.
- Analysis of change in VAS for pain score from baseline to every 24 weeks using MMRM analysis.

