- Analysis of change in EQ-5D scores from baseline to every 24 weeks using MMRM analysis.
- Analysis of change in T25W scores from baseline to every 24 weeks using MMRM analysis.
- Analysis of change in mRS scores from baseline to every 24 weeks using MMRM analysis.
- Analysis of change in ZBI scores from baseline to every 24 weeks using MMRM analysis.
- Analysis of change in EDSS scores from baseline to every 24 weeks using MMRM analysis.
- Analysis of change in visual function (Snellen chart) scores from baseline to every 24 weeks using MMRM analysis.
- Analysis of change in low-contrast visual acuity (Low-contrast Sloan letter chart [LCSLC]) scores from baseline to every 24 weeks using MMRM analysis.

The MMRM will include treatment group, protocol-specified visit, treatment-by-visit interaction as fixed effects; the baseline measurements and stratification factors as a covariate; and visit as a repeated measure. The unstructured covariance matrix will be assumed in the model.

If the unstructured covariance matrix does not converge, the length of the observation interval will be limited (e.g. to Week 96) and/or compound symmetric structure will be used. If treatment-by-visit interaction is not statistically significant, the full model will be kept.

If the normality assumption for other secondary variables does not hold, GEE or Generalized Linear Mixed-effect model analysis will be used. The assessment will be performed prior to unblinding.

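### Under SAP 7.0 the EDSS, mRS, walking and vision analyses omit most values after a confirmed relapse, unequally by arm, with no sensitivity analysis such as pain and fatigue receive

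*SAP*

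**What the plan says.** **Period.** For efficacy, SAP 4.2 closes the double-blind period at the earliest of four dates. One of them is "2) the day before the first treatment in the extension period". OLE Week 0 is a dosing day, so its assessments fall outside the period. For by-visit summaries the same section states that "extra visit at relapsing, and the end of the study are out of scope".

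**Model.** SAP 4.10.3 limits the secondary efficacy analyses to the double-blind period. SAP 4.10.1.3 says that a "Mixed-effects model repeated measures analysis incorporating all data in double blind period will be used". SAP 4.10.3.2 lists "Analysis of change in EDSS scores from baseline to every 24 weeks using MMRM analysis", with matching entries for mRS, timed 25-foot walk (T25W), Snellen and low-contrast acuity. Visit enters the model as the protocol-specified visit.

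**Contrast with pain and fatigue.** SAP 4.10.3.1 notes that "VAS for Pain and fatigue are assessed at OLE baseline visit for patients entering into OLE". If Week 24 is missing, it substitutes an OLE-baseline or withdrawal value from study days 85 to 252. No such analysis is planned for the disability measures.

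**Data collected.** Protocol 4.5.3.2 and Appendix 1 Table 7 schedule EDSS/FSS, visual function, mRS and T25W at OLE Week 0, with the injection given last. For patients with a confirmed relapse, Protocol 4.3.2.2 allows OLE to start at Day 31 or later, counting onset as Day 1.

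**Later text.** Protocol Version 10, section 6.5.2, adds time to EDSS worsening. It runs the EDSS analyses for the double-blind period and for double-blind and OLE combined. SAP 7.0 was written against protocol 8.2AB and has neither.

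**The concern.** Protocol 1.1.1 says that "disability in NMO is directly tied to the number and severity of relapses", and that secondary progression is uncommon. A drug that prevents relapses should therefore protect function mainly by that route. Yet a confirmed relapse is the event that moves a patient out of the analysed period. Disability is scheduled only every 24 weeks, so a patient who enters OLE before Week 24 gives the model no post-baseline disability value.

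MMRM does not repair this. Departure follows neurological worsening, and a 1.0-point EDSS rise is itself one of the relapse criteria (Protocol 4.5.1.8). If the worsened score is not in the model, missing outcomes are in effect predicted from patients still under double-blind follow-up. More placebo than satralizumab patients are expected to relapse, so the loss is unequal and pulls the arms together. What is at stake is whether the trial can describe the effect of relapse prevention on lasting disability.

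**Working it through.** **Inputs (Protocol 6.2, SAP 4.14).** Placebo ARR 1.35; variance/mean ratio √2; placebo hazard h = 1.1295 per year; hazard ratio 1.0 for 2 months, then 0.25; 90 patients randomised 2:1 (60 and 30).

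**Reproducing the plan's figure.** The Gamma-Poisson zero probability is P0 = (√2)^(−1.35/(√2−1)) = 0.3232, and −ln P0 = 1.1295. Both agree with the stated 32.3% and 1.1295.

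**First relapse by time t (years), no dropout.**
- Placebo: 1 − exp(−1.1295 t)
- Satralizumab, t > 2/12: 1 − exp(−1.1295 × [2/12 + 0.25 × (t − 2/12)])
- Week 24, t = 168/365.25 = 0.460: 1 − exp(−0.5195) = 40.5% (12.2 of 30) against 1 − exp(−0.2711) = 23.7% (14.2 of 60)
- Week 48, t = 336/365.25 = 0.920: 1 − exp(−1.0390) = 64.6% against 1 − exp(−0.4009) = 33.0%

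**Already in OLE before the visit.** A relapser leaves only when OLE dosing starts, so evaluate the same formulas at u = t − gap. I assume that every confirmed relapser enters OLE. The 31-day gap stands for the documented minimum; reading Day 31 as 30 days after onset moves these shares by at most about 0.2 percentage points. Gaps of 60 and 90 days are assumptions.

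| Gap (days) | Week 24: placebo / satralizumab | Week 48: placebo / satralizumab |
|---|---|---|
| 31 | 34.5% / 21.9% | 61.1% / 31.4% |
| 60 | 28.4% / 20.1% | 57.4% / 29.9% |
| 90 | 21.4% / 18.2% | 53.3% / 28.2% |

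For example, at 31 days before Week 24, u = 0.375, giving 1 − exp(−0.4237) = 34.5% and 1 − exp(−0.2471) = 21.9%.

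**Illustration of the bias.** Suppose each first relapse leaves a lasting EDSS rise J = 1.0 (an assumption). Write S(t) for the relapse-free probability.
- With all post-relapse values kept, the difference (satralizumab minus placebo) is J × [S(t) placebo − S(t) satralizumab]: −0.17 at Week 24 and −0.32 at Week 48.
- In observed double-blind data, each arm's mean rise is J × [1 − S(t)/S(u)]. With a 31-day gap this is 0.024 for satralizumab and 0.091 for placebo at either visit, a difference of −0.07. For 60 and 90 days it is −0.12 and −0.18.
- Share of the full difference retained at 31 / 60 / 90 days: 40 / 74 / 105% at Week 24 and 21 / 39 / 56% at Week 48.

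The differences scale with J: at Week 48 the full difference is −0.16 for J = 0.5 and −0.63 for J = 2.0. This is an observed-case calculation. At Week 48 the MMRM also borrows from Week 24 values, but those of later relapsers were mostly recorded before the relapse.

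**The case against.** A reader might infer that these analyses exclude all disability caused by relapse, or that the model sees almost none of it. The documents do not support that.

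- Protocol 4.3.2.1 says: "Patients who experienced a relapse during the double-blind period should continue the double-blind period regardless of rescue therapy unless the patient experiences a relapse" that the committee confirms as protocol-defined. Patients with unconfirmed relapses stay in, and their later scheduled values count.
- The SAP closes the period at the first OLE dose, not at relapse, so a scheduled visit in the gap counts. Hence the retained shares above: with a 90-day gap nothing is lost at Week 24 in this illustration.
- The out-of-scope sentence is written for by-visit summaries. Its extension to the MMRM follows from the use of protocol-specified visits but is not stated. The loss of OLE Week 0 does not depend on it.
- The extra relapse visit schedules only EDSS/FSS. For mRS, T25W and low-contrast acuity there is no relapse-visit value to exclude.

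A reader might also infer that no document addresses the problem. Protocol Version 10 does so for EDSS, through time to worsening and the combined-period analyses. It does not for the other four measures, and its section 6.9 still describes the MMRM for continuous secondary endpoints as using double-blind data.

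Two further points stand. These endpoints lie outside the testing hierarchy in SAP 4.10.1.4, and the bias runs toward no difference, so no false claim of benefit arises from it. The illustrated differences for rises of 0.5 to 1.0 point (0.08 to 0.32) are also smaller than one 0.5-point EDSS step. These points limit the consequence; they do not explain why pain and fatigue receive a safeguard that the disability measures lack.

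**Conclusion.** The concern holds in limited form. Under SAP 7.0 the MMRMs for all five measures omit most post-relapse values after a confirmed relapse, and the omission differs by arm: 34.5% against 21.9% of patients gone before Week 24, and 61.1% against 31.4% before Week 48, at a 31-day gap. The direction is toward concealing a benefit on disability. How much is concealed depends on the gap and on the assumed lasting rise, neither of which the documents fix beyond the Day 31 minimum. The shares also assume the design hazards, no dropout and OLE entry by every confirmed relapser. The primary analysis, its power and the control of type I error are unaffected. The gap is worth closing because the values are already collected before OLE dosing.

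**What to change.** In SAP 4.10.3.2, add a supplementary MMRM for EDSS, mRS, T25W, Snellen and low-contrast acuity, reported beside the planned one. When a scheduled value is missing, use the OLE Week 0 (pre-dose) or Withdrawal Visit value.

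Map it to Week 24 by the existing days 85 to 252 window. SAP 4.10.3.1 covers only Week 24, so later visits need a stated rule. The midpoint approach that SAP 4.2 uses for the all-satralizumab summaries fits: Weeks 24, 48 and 72 are days 169, 337 and 505, the midpoints are days 253 and 421, and Week 48 would take days 253 to 420.

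Bring the SAP into line with the Version 10 EDSS analyses. I would not add a version using the relapse-visit EDSS: it records acute worsening and would largely restate the primary endpoint.

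**Cost.** One extra analysis per measure and no new data. Post-relapse values reflect rescue therapy and variable timing. Recovery is partial: an OLE Week 0 before day 85 is still not used (with a 30-day gap, relapses before about day 55, or 1 − exp(−1.1295 × 55/365.25) = 15.6% of each arm), and a patient mapped to one visit still lacks later ones. Version 10 records that the double-blind period is complete, so if the treatment code has been opened the analysis should be labelled post hoc.

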3.2.3 Rationale for Test Product Dosage

Based on PK and PD assessments in Phase I studies with satralizumab and anecdotal efficacy data from investigational studies of tocilizumab, 120 mg Q4W will be used as the maintenance dose of satralizumab in this study.

The mean trough level of satralizumab 120 mg SC Q4W in steady state in study SA-105JP was 20.3 ± 6.13 $\mu\text{g/mL}$ and the computed mean trough level of tocilizumab 8 mg/kg IV Q4W in steady state was 9.7 ± 11 $\mu\text{g/mL}$ (Frey N et al. 2010). Based on these data, the PK of satralizumab 120 mg SC Q4W was higher than that of tocilizumab 8 mg/kg IV Q4W. However, the patients enrolled to the Phase 1b (SA-105JP) were all Japanese RA patients and mean body weight of the patients was 54.1 ± 10.8 kg. On the other hand, the mean body weight of patient in the Phase 3 studies of tocilizumab was 67 to 73 kg. The computed PK of satralizumab 120 mg SC Q4W in RA patients (based on a body weight of 75 kg) is 8.2 $\mu\text{g/mL}$, which is comparable to tocilizumab 8 mg/kg IV Q4W.

This dose is appropriate based on the following considerations:

Results from Phase 1 single-dose study in healthy subjects and multiple dose study in patients with rheumatoid arthritis showed that satralizumab 120 mg Q4W inhibited IL-6 signaling completely, whereas lower doses (30, 60 mg Q4W) did not.

Systemic inflammatory condition is not expected in patients with NMO and NMOSD compared to RA patients, therefore, inflammatory parameter such as C-reactive protein (CRP) and IL-6 is within normal range in patients with NMO and NMOSD.

Therefore, satralizumab 120 mg Q4W is expected to inhibit IL-6 signaling completely in patients with NMO and NMOSD.

IV tocilizumab 8 mg/kg Q4W, trough level of which is comparable to satralizumab 120 mg Q4W, showed preliminary clinical efficacy in the investigational case reports in patients with NMO and NMOSD. In addition, the PK/PD correlation between tocilizumab and satralizumab is comparable.

Satralizumab has been investigated in 2 studies, including one Phase 1 single ascending dose study in Caucasian and Japanese healthy volunteer (SA-001JP) and one Phase 1b multiple dose study in Japanese RA patients (SA-105JP).

For the NMO Studies BN40890 and BN40900 (SA-307JG and SA-309JG), satralizumab 120 mg SC Q4W was selected based on the assumptions below.

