For pharmacokinetic endpoints, concentrations will be analyzed using all reported decimal places, and displayed to the same number of decimal places as recorded in the database. If any samples are collected outside of the protocol defined time window (Appendix 1 in the protocol), the relevant values will be excluded for the calculation of descriptive statistics. Furthermore, if the samples are collected more than 6 weeks after the last study drug administration, the relevant values will be excluded for the calculation of descriptive statistics considering the half-life of IgG. Descriptive statistics will include number of the subjects, geometric mean, geometric coefficient of variation (CV) and the 95% confidence interval for the geometric mean of the concentrations, as well as arithmetic mean, SD, median, minimum, and maximum of SA237 concentrations will be calculated by visit and per defined time window post-dose according to the Pharmacokinetics Per-Protocol Set (PK-PPS). The CV will be presented with 1 decimal place. For the calculation of descriptive statistics, a serum concentration below limit of quantification will be substituted by half of lower limit of quantification (i.e. LLOQ/2). If more than half of the measured values are BLQ at any blood sampling time point, the statistics will not be tabulated for that time point and will be shown as "N.C.".

TP-GDO-WW-016-01 Confidential Version 7.0 Effective Date: 28Aug13 Version Date: 28NOV2018

Page 11 of 60

For immunogenicity, below rules will be applied to neutralizing antibodies:

- Except baseline measurement, neutralizing antibodies will be assessed only if anti-SA237 antibody results are positive.
- If SA237 concentration is over 1 ug/mL, the data of the neutralizing antibodies will be excluded for the calculation of descriptive statistics. High concentrations of SA237 could lead to false negative results in the neutralizing antibody analysis

Changes from baseline in categorical data will be summarized using shift tables where appropriate.

P-values greater than or equal to 0.001, in general, will be presented to three decimal places. P-values less than 0.001 will be presented as "<0.001".

Confidence intervals will be presented to one more decimal place than the raw data.

The Confidence Interval for hazard ratio will be calculated based on the Wald type and the relapse rate Confidence Interval will be provided using Kaplan Meier method with a LOGLOG transformation.

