- > The numbers and proportions of patients with positive/negative anti-SA237 antibodies and neutralizing antibodies will be presented at Week 0 and Q4W in SA237 group by visit.
 - A by-subject listing of anti-SA237 antibody (confirmatory judgment (positive/negative), titer, ratio of peak titer/baseline titer, and ADA subgroup), neutralizing judgment (positive/negative)), and adverse events in the subject having anti-SA237 antibody at least once at any point in time.

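### Neutralising-antibody positives found above 1 µg/mL of drug are left out of the by-visit table, although the SAP's stated reason discredits only negatives

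*SAP*

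**What the plan says.** SAP 4.2 sets two rules for neutralising antibodies. The first limits who is tested: "Except baseline measurement, neutralizing antibodies will be assessed only if anti-SA237 antibody results are positive". The second limits what is summarised: when the SA237 concentration is over 1 µg/mL, "the data of the neutralizing antibodies will be excluded for the calculation of descriptive statistics". The reason follows directly: "High concentrations of SA237 could lead to false negative results in the neutralizing antibody analysis". The exclusion carries no condition on the result, and no concern about false positives is raised.

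SAP 4.13 then plans a table for the SA237 group, by visit, of the numbers and proportions with "positive/negative anti-SA237 antibodies and neutralizing antibodies will be presented at Week 0 and Q4W". It gives no inconclusive category, no exception for positives and no denominator of its own. The same section keeps the neutralising judgement in a by-subject listing for anyone who is ever antibody-positive.

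SAP 4.2 also sets the general rule for percentages. The default denominator is the whole treatment group within the population of interest. The same paragraph speaks of a denominator suited to the purpose of the analysis, so the choice for this table is not settled.

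**The concern.** The rule is wider than its reason. If drug in the sample can hide a neutralising antibody, a negative at high drug level is uninformative. A positive at high drug level was detected despite that interference, and nothing in the SAP calls it into question. Removing it discards evidence on immunogenicity, which is a protocol objective (Protocol 2.5).

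The excluded samples are also not a random subset. Protocol 5.1.1.6 reports lower exposure in antibody-positive patients, so drug level is partly a consequence of antibody status. A table restricted to samples with low drug level is filtered on something the antibodies influence, and a reader cannot see how many samples were removed.

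Antibodies were not rare. The same section reports them in 71% of satralizumab patients in this study's double-blind period, and says that most of those found in the Phase 1 single-dose study were neutralising.

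**Working it through.** **1. Rule against reason.**

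| SA237 in sample | Result | Does the stated reason cast doubt on it? | Does the rule exclude it? |
|---|---|---|---|
| ≤ 1 µg/mL | positive | no | no |
| ≤ 1 µg/mL | negative | no | no |
| > 1 µg/mL | negative | yes | yes |
| > 1 µg/mL | positive | no | yes |

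Only the last row is out of line.

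**2. Effect under each denominator.** Let P_L and N_L be positives and negatives at or below the limit, P_H the positives above it, and T the number in the SA237 group.

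- Treatment-group denominator (the SAP 4.2 default): the table shows P_L/T, whereas the positives found are (P_L + P_H)/T. The shortfall is P_H/T.
- Evaluable-only denominator: the table shows P_L/(P_L + N_L). This estimates the rate among all tested patients only if neutralising status is unrelated to being above or below 1 µg/mL.

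**3. How many tested samples might exceed 1 µg/mL.** Inputs from Protocol 3.2.3: "The mean trough level of satralizumab 120 mg SC Q4W in steady state in study SA-105JP was 20.3 ± 6.13" µg/mL (mean body weight 54.1 kg), and "The computed PK of satralizumab 120 mg SC Q4W in RA patients (based on a body weight of 75 kg) is 8.2" µg/mL. SAP 4.12 places sampling before dosing, so trough is the right comparison. These means are 8.2 to 20.3 times the limit.

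Lognormal model with mean m and coefficient of variation CV: σ² = ln(1 + CV²), μ = ln(m) − σ²/2, P(X > 1) = Φ(μ/σ). The CVs are 30% (6.13/20.3), 60% (assumed) and 113% (11/9.7, the tocilizumab figure in the same section). The documents say exposure was lower in antibody-positive patients but not by how much, so the fraction is assumed.

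| Exposure as fraction of mean | m (µg/mL) | P(> 1), from m = 8.2 | P(> 1), from m = 20.3 | Range |
|---|---|---|---|---|
| 100% | 8.2; 20.3 | 96.9–100% | 99.8–100% | 97–100% |
| 50% | 4.1; 10.15 | 86.4–100% | 98.2–100% | 86–100% |
| 25% | 2.05; 5.08 | 63.1–98.9% | 90.9–100% | 63–100% |
| 10% | 0.82; 2.03 | 20.6–26.3% | 62.7–98.8% | 21–99% |
| 5% | 0.41; 1.02 | 0.1–7.6% | 33.1–46.1% | 0–46% |

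Example: m = 2.05 and CV = 1.134 give σ² = 0.827, σ = 0.909, μ = 0.304 and Φ(0.335) = 0.631. The first row describes an average RA patient, not the antibody-positive samples that are actually tested.

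**4. Illustration (all inputs assumed).** Take 100 antibody-positive samples, 60 of them above the limit, a true neutralising rate of 50% on both sides of it, and assay sensitivity of 0.6 above it and complete below it.

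- At or below the limit: 40 samples, 20 positive and 20 negative.
- Above it: 60 × 0.5 × 0.6 = 18 positive and 60 − 18 = 42 negative.
- The SAP rule counts 20 positives and omits 18.
- Three categories: 38 positive, 20 negative and 42 inconclusive of 100.
- Keeping the positives but dropping the 42 inconclusives: 38/(38 + 20) = 66%, against a true 50%.
- Keeping every result as reported: 38/100 = 38%.

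Across shares above the limit of 30% to 90%, true rates of 50% or 80% and sensitivities of 0.2 or 0.6, the omitted positives run from 3 to 43 per 100 samples. With equal rates on both sides, as assumed here, the evaluable-only figure (20/40 = 50%) is unbiased. Step 2 says when that fails.

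**The case against.** The strongest defence is that excluding every result outside an assay's tolerance range does not depend on the result, whereas keeping positives and setting negatives aside does. This stands in one respect. A rate that drops only the inconclusives is inflated, as the 66% against 50% shows. It does not defend the planned table, because a three-way count over all tested patients removes nobody.

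The documents also do not describe the assay's format or drug-tolerance validation. That a positive above 1 µg/mL can be trusted is therefore an inference from the SAP's own reason, which names false negatives alone.

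Three limits on the harm stand in full. The results remain in the by-subject listing. Week 0 samples precede the first dose (SAP 4.12). The immunogenicity endpoints and the efficacy subgroups use anti-drug antibody status, not neutralising status.

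A reader who sets 1 µg/mL beside 8.2–20.3 µg/mL might infer that nearly all results are lost, or that the proportions rest mainly on patients whose drug level has collapsed. The documents do not support either reading. The troughs are RA figures for all patients, and only 2 of 33 patients in SA-105JP had antibodies (Protocol 5.1.1.6). Post-baseline neutralising tests are confined to antibody-positive samples, where exposure was lower by an amount not stated. Nor can it be said that the table would report a very high percentage, because that needs an evaluable-only denominator, which is not the SAP's default.

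**Conclusion.** The point holds as a minor reporting defect. As written, the rule removes positive results that its own reason does not question, and the table has no place for inconclusive ones. The direction of the effect depends on an unsettled denominator: understatement of positives under the default, or a subset selected on drug level under the alternative.

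Its size is unknown. The ranges in the working rest on assumed exposure fractions, assumed spread and a lognormal shape, and run from almost no samples affected to all of them. The finding rests on the text of SAP 4.2 and 4.13, not on any of those percentages. No primary or key secondary result depends on it.

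**What to change.** In SAP 4.2, replace the blanket exclusion with a classification: a positive counts as positive at any drug level, and a negative with SA237 above 1 µg/mL is inconclusive. In SAP 4.13, report positive, negative and inconclusive at each post-baseline visit, with all antibody-positive patients tested at that visit as the stated denominator. Do not compute a rate that leaves out only the inconclusives. The Week 0 row can stay as it is, since no drug has been given.

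The cost is one amended rule and one extra table row; no new data are needed. The downside is that the positive proportion becomes a lower bound, because some inconclusive samples will be missed positives. A footnote should say so.
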